10.4.3 Derivations of Immunogenicity Endpoints

In numerical calculation of HPV type-specific GMTs, anti-HPV titer results reported as "less than [lower limit of quantification (LLOQ)]" or "<[LLOQ]", where [LLOQ] corresponds to the lower limit of quantitation of the cLIA assay for the relevant HPV type, will be replaced by a numerical number equal to half of LLOQ of the relevant HPV type.

10.5 Analysis Populations

10.5.1 Immunogenicity Analysis Population

The PPI population will serve as the primary population for the analysis of immune response to each of the HPV Types 6, 11, 16, 18, 31, 33, 45, 52, and 58 in this study. The PPI population is HPV type-specific and consists of all allocated participants who:

1. Were seronegative to the appropriate HPV type at Day 1;
2. Have received all 3 vaccinations with the correct dose of 9vHPV vaccine within acceptable day ranges around the planned vaccination visits as shown in [Table 4](#);
3. Have provided serum sample within 21 to 49 days post Dose 3;
4. Have no protocol deviations that could interfere with the evaluation of participant's immune response to 9vHPV vaccination. At Day 1, participants 9 to 15 years of age must satisfy inclusion criterion 4 (ie, "Has not yet had coitarche and does not plan on becoming sexually active during the vaccination period (Day 1 through Month 7)" as specified in Section 6.1.

To be included in the PPI population for HPV 6 and 11, participants must be seronegative to both HPV 6 and 11 at Day 1. To be included in the PPI population for any other vaccine HPV type, participants need to be seronegative at Day 1 only for the HPV type being analyzed.

The final determination of protocol deviations that could interfere with the evaluation of participant's immune response to 9vHPV vaccination, and thereby the composition of the PPI population, will be made prior to the final database lock.

Details on the approach to handling missing data are provided in Section 10.6 (Statistical Methods).

Table 4 Acceptable Day Ranges for Vaccination Visits

Dose of 9vHPV vaccine Scheduled for Injection	Protocol Specified Visit Window	Day Range for Inclusion in Statistical Analysis (Relative to Day 1 ^a)
Dose 1	Day 1 ^a	0
Dose 2	Month 2 ±3 weeks	36 to 84
Dose 3	Month 6 ±4 weeks	148 to 218

^a Day 1 refers to the date when Dose 1 of 9vHPV vaccine is injected. For post Day 1 vaccinations, the day ranges for inclusion in the statistical analysis are wider than the protocol specified visit windows primarily to account for differences at the sites in counting months (eg, 1 calendar month versus 30 days versus 4 weeks).

10.5.2 Safety Analysis Populations

The APaT population will be used for the analysis of safety in this study. The APaT population consists of all allocated participants who received at least one dose of 9vHPV vaccine and have provided safety data at any time during the study.

10.6 Statistical Methods

Statistical analyses of safety described in Section 10.6.2. Immunogenicity results that will be deemed to be statistically significant after consideration of the Type I error control strategy are described in Section 10.8 (Multiplicity).

10.6.1 Statistical Methods for Immunogenicity Analyses

A summary of the analysis strategy for key primary and secondary immunogenicity endpoints is shown in [Table 5](#).

The primary immunogenicity hypothesis will be addressed by calculating point and 95% CI estimates of percent seroconversion, to be derived from the point and 95% CI estimates of the proportion of participants who seroconverted (ie, point estimate and 95% CI of proportion \times 100%). Specifically, for each HPV type:

- The point estimate of proportion of participants who seroconverted to a particular HPV type is the ratio of the number of PPI-eligible participants for that particular HPV type who seroconverted to the relevant HPV type over the total number PPI-eligible participants for that particular HPV type who had evaluable Month 7 serology result based on serum sample collected within 21 to 49 days post Dose 3.
- The corresponding 95% CI estimate of proportion will be derived based on exact binomial calculations.
- The statistical criterion for acceptable anti-HPV seroconversion requires the lower limit of the 95% CI of the percent of participants who seroconverted to be greater than 90% for each HPV type.

The secondary immunogenicity objective will be addressed by calculating point and 95% CI estimates of GMTs. For each HPV type:

- The point estimate of GMT will be calculated by taking the anti-natural-logarithm of the arithmetic mean of the natural-logarithm-transformed anti-HPV titers.
- The two-sided 95% CI estimate of GMT will be calculated by taking the anti-natural-logarithm of the two-sided 95% CI estimate of the mean of the natural-logarithm-transformed anti-HPV titers based on the t-distribution.

Table 5 Analysis Strategy for Key Immunogenicity Endpoints

Endpoint	Primary vs. Supportive Approach	Statistical Method	Analysis Population	Missing Data Approach
Primary Hypothesis				
Percent seroconversion	Primary	Point and 95% CI estimation of binomial proportion based on Clopper-Pearson (exact) method	PPI	Observed data only
Secondary Objective				
GMTs	Primary	Point and 95% CI estimation of means based on t-distribution	PPI	Observed data only

CI=confidence interval; GMT=geometric mean titer; PPI=Per-Protocol Immunogenicity.

10.6.2 Statistical Methods for Safety Analyses

Safety will be assessed by clinical review of all safety data collected after each vaccination.

Since this study is a single-arm study with no comparator arm, safety assessments will be descriptive in nature and will include calculation of proportions of participants with any AEs, injection-site AEs, systemic AEs, SAEs, vaccine-related SAEs, and discontinuations due to an AE within Day 1 to Day 15 following receipt of 9vHPV vaccination; in addition, 95% CI values for AEs will be provided for SAEs, injection site AEs, systemic AEs, and vaccine-related systemic AEs. Oral temperatures recorded on the VRC will be summarized.

10.7 Interim Analyses

No interim analyses are planned for this study.

10.8 Multiplicity

The criterion for successful demonstration of the primary immunogenicity hypothesis requires demonstration of the lower limit of the 95% CI of the percent of participants who seroconverted to be greater than 90% for each (ie, all) HPV Types 6, 11, 16, 18, 31, 33, 45, 52, and 58. The corresponding tests of hypothesis for each of these HPV types will be conducted at 1-sided Type I error level of 0.025 (see Section 10.9; Sample size and Power Calculations). No multiplicity adjustment is required on the 0.025 1-sided Type I error level since success is required for all of the 9 HPV types being tested.

10.9 Sample Size and Power Calculations

10.9.1 Sample Size and Power for Immunogenicity Analysis

This study will enroll 200 participants to be vaccinated with 9vHPV vaccine and has approximately 97% power at an overall one-sided 2.5% alpha-level (ie, 1-sided Type I error equal to 0.025) to establish that the 9vHPV vaccine induces among participants >90% seroconversion to HPV Types 6, 11, 16, 18, 31, 33, 45, 52, and 58 at 4 weeks post Dose 3. The overall study power corresponding to the sample size of 200 participants is based on the following assumptions: 1) approximately 24% to 34% of participants enrolled will be ineligible for the per-protocol analysis of seroconversion to the 9 HPV types; and 2) the underlying true seroconversion across the 9 HPV types is $\geq 98\%$ (see [Table 6](#)). The power calculation was based on the exact binomial method of Clopper and Pearson [Clopper, C. J. and Pearson, E. S. 1934] and was done using PASS 2008. The minimum criterion for success for each HPV type is that the lower limit of the 95% CI of percent seroconversion be >90%. Given the number of participants eligible for the per-protocol analysis expected from this study, this may occur when the point estimate of percent seroconversion observed during the study is >96% in each of the 9 HPV types. The numbers of seroconversions across the 9 HPV types relative to the expected number of participants eligible for the per-protocol analysis that will yield a point estimate of seroconversion >96% are shown in [Table 6](#).

Table 6 Power for Testing the Primary Immunogenicity Hypothesis

HPV Type	Participants Enrolled (N)	Expected to be Observed in the Study			Assessment of Power for Testing H ₀ : P = P ₀ versus H _a : P > P ₀					Minimum Number of Seroconversions Needed to Attain a Point Estimate of Percent Seroconversion >96% ^c
		Exclusions from PPI Analysis ^a	Evaluable for PPI Analysis (n)	Percent Sero-conversion ^a	P ₀ ^b	P _E ^b	Type I Error (α)		Power	
							Target	Expected Actual		
6	200	34%	132	98.3%	0.90	0.98	0.025	0.018	0.9826	127
11		34%	132	99.7%		0.99		0.018	0.9996	127
16		30%	140	100%		0.99		0.011	0.9994	135
18		27%	146	99.2%		0.99		0.018	0.9999	140
31		25%	150	99.0%		0.99		0.014	0.9999	144
33		26%	148	99.1%		0.99		0.016	0.9999	142
45		24%	152	98.4%		0.98		0.012	0.9881	146
52		32%	137	99.4%		0.99		0.013	0.9995	132
58		31%	139	99.4%		0.99		0.012	0.9995	134
Overall Study Power:									0.9687	
^a Historical data from the Asian cohort (Korean and Taiwanese) of the V503-001 study. ^b For each HPV type, the null hypothesis that the seroconversion proportion is 0.90 (P=P ₀) is being tested against the alternative hypothesis that the seroconversion proportion is greater than 0.90 (P>P ₀). In the calculation of power corresponding to the expected number of participants evaluable for the PPI analysis, a proportion of seroconversion that is expected (P _E) to be observed during the study is required. The values of P _E used in the calculation of power are obtained from the historical percent seroconversion observed from the Asian cohort of the V503-001 study. ^c Assuming the number of participants contributing to the PPI analysis is equal to (n), a point estimate of percent seroconversion >96% will yield a corresponding lower limit of 95% CI of percent seroconversion >90%. CI=confidence interval; PPI=Per-Protocol Immunogenicity.										

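### Do the three Table 6 counts that miss their own >96% heading (HPV 18, 31, 33), or the >96% benchmark itself, call for a change to the plan?

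*Combined protocol and SAP*

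**What the plan says.** Section 10.9.1 states the rule for each type: "The minimum criterion for success for each HPV type is that the lower limit of the 95% CI of percent seroconversion be >90" per cent. Sections 4, 10.1, 10.6.1 and 10.8 give the same rule, and Table 5 names the Clopper-Pearson interval as the method. Section 10.8 adds that "The corresponding tests of hypothesis for each of these HPV types will be conducted at 1-sided Type I error level of 0.025", with success required on all nine types. On power, Section 10.9.1 says "The power calculation was based on the exact binomial method of Clopper and Pearson", and footnote b to Table 6 sets "the null hypothesis that the seroconversion proportion is 0.90".

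The section then translates the rule into an observed percentage. At the expected numbers evaluable, it says, "this may occur when the point estimate of percent seroconversion observed during the study is >96% in each of the 9 HPV types". It refers to Table 6 for the counts "that will yield a point estimate of seroconversion >96% are shown in" that table, and the column itself is headed "Minimum Number of Seroconversions Needed to Attain a Point Estimate of Percent Seroconversion >96" per cent. Footnote c, which assumes that the number analysed equals the planned n, says that "a point estimate of percent seroconversion >96% will yield a corresponding lower limit of 95% CI of percent seroconversion >90" per cent.

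**The concern.** Two things catch the eye. First, dividing the printed count by n gives a figure at or below 96% in three rows, so those cells contradict both the heading and the sentence that introduces the table. Second, the column stands next to the alpha and power columns and uses the word minimum, so a reader may take it for the critical count of each test. It is not: the criterion is already met one seroconversion lower in every row.

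If the column were the decision rule, this would matter. Nine types must all succeed, and raising each threshold by one count would bring overall power below the stated 97%. If the three low cells had fallen under the true critical count, the table would have shown failing results as successes.

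**Working it through.** **Inputs.** From Table 6: n per type as printed, P0 = 0.90, and P_E = 0.98 for HPV 6 and 45 and 0.99 for the other seven. From Sections 10.8 and 10.9.1: one-sided alpha 0.025 and the exact binomial method. The printed n for HPV 52 and 58 (137 and 139) are used; the rounded exclusion percentages of 32% and 31% would give 136 and 138.

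**Step 1: reproduce the plan's alpha and power.** The critical count c is the smallest x with P(X ≥ x | n, 0.90) ≤ 0.025. It is also the smallest x whose Clopper-Pearson lower limit L(x) = Beta⁻¹(0.025; x, n − x + 1) exceeds 0.90. Then alpha = P(X ≥ c | n, 0.90) and power = P(X ≥ c | n, P_E).

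| HPV | n | c (c/n) | L(c) | L(c − 1) | Alpha: computed / printed | Power: computed = printed |
|---|---|---|---|---|---|---|
| 6 | 132 | 126 (95.45%) | 0.9037 | 0.8938 | 0.0183 / 0.018 | 0.9826 |
| 11 | 132 | 126 (95.45%) | 0.9037 | 0.8938 | 0.0183 / 0.018 | 0.9996 |
| 16 | 140 | 134 (95.71%) | 0.9091 | 0.8997 | 0.0109 / 0.011 | 0.9994 |
| 18 | 146 | 139 (95.21%) | 0.9037 | 0.8949 | 0.0179 / 0.018 | 0.9999 |
| 31 | 150 | 143 (95.33%) | 0.9062 | 0.8976 | 0.0140 / 0.014 | 0.9999 |
| 33 | 148 | 141 (95.27%) | 0.9050 | 0.8963 | 0.0159 / 0.016 | 0.9999 |
| 45 | 152 | 145 (95.39%) | 0.9074 | 0.8989 | 0.0124 / 0.012 | 0.9881 |
| 52 | 137 | 131 (95.62%) | 0.9071 | 0.8976 | 0.0133 / 0.013 | 0.9995 |
| 58 | 139 | 133 (95.68%) | 0.9084 | 0.8990 | 0.0117 / 0.012 | 0.9995 |

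The product of the nine unrounded powers is 0.9686; the product of the nine printed powers is 0.9687, the printed overall figure. The last column of Table 6 was not needed for any of this.

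**Step 2: test the last column against its heading.** The smallest count for a point estimate above 96% is the smallest integer strictly greater than 0.96 × n.

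| HPV | 0.96 × n | Smallest count above it | Printed | Printed / n | L(printed) |
|---|---|---|---|---|---|
| 6, 11 | 126.72 | 127 | 127 | 96.21% | 0.9138 |
| 16 | 134.40 | 135 | 135 | 96.43% | 0.9186 |
| 18 | 140.16 | **141** | **140** | 95.89% | 0.9127 |
| 31 | 144.00 | **145** | **144** | 96.00% | 0.9150 |
| 33 | 142.08 | **143** | **142** | 95.95% | 0.9139 |
| 45 | 145.92 | 146 | 146 | 96.05% | 0.9161 |
| 52 | 131.52 | 132 | 132 | 96.35% | 0.9169 |
| 58 | 133.44 | 134 | 134 | 96.40% | 0.9181 |

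Three cells are one too low for the heading and six are right. All nine printed counts have a lower limit between 0.9127 and 0.9186, above 0.90.

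**Step 3: test the sufficiency statement.** At the tabulated n, the smallest counts above 96% give lower limits from 0.9138 (127/132) to 0.9239 (145/150). Footnote c is therefore true in every row. It also has room to spare: among n from 60 to 200, the largest n at which it fails is 84 (81/84, lower limit 0.8992). With 200 enrolled, that means 116/200 = 58% excluded, against 24% to 34% assumed.

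**Step 4: size of a misreading.** If the printed counts were used as the thresholds, the product of the powers would be 0.905. With a strict >96% rule it would be 0.897. The documents prescribe neither.

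**The case for a change.** The strongest case for a correction is that the slip is real and cannot be explained away. Rounding does not rescue the cells, because a value that rounds to 96% still does not exceed it, and the n in each row is intact, since it reproduces that row's alpha and power. Every printed count is exactly one above the critical count, a pattern that fits all nine rows, whereas the heading fits only six. The column may therefore have been built on some other basis than the heading states; the documents do not say. It is also the only place where the nine-way criterion is accompanied by counts, and those counts do not match the alpha and power beside them: with 127 as the threshold for HPV 6, power would be 0.9498, not 0.9826.

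What stands is that three cells are mislabelled by one. The rest does not amount to an error. The heading ties the minimum to reaching 96%, not to meeting the criterion. The text says only that success may follow above 96%, and footnote c claims sufficiency alone; both are correct at the planned n. Nothing says that these counts generated alpha and power, and the section gives all the inputs needed to recompute both. The power loss in Step 4 describes a use that the plan does not make.

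**Conclusion.** No change to the plan follows. The three entries (140, 144 and 142 where the heading implies 141, 145 and 143) are a clerical slip, and the >96% benchmark is a rounded sufficient condition that the plan describes as such.

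The analysis under Section 10.6.1 computes an exact interval from the observed count and the observed type-specific number evaluable, so the Table 6 counts never enter the decision. Even at exactly the planned n, each printed count, including the three low ones, meets the criterion. Correcting them would alter no sample size, alpha, power, decision or conclusion.

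This rests on the lower confidence limit remaining the decision rule, as the plan states throughout. The recomputed lower limits use the printed n and the Clopper-Pearson method. The overall power also uses the printed P_E values and multiplies the nine powers, which reproduces the plan's own overall figure.

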10.9.2 Sample Size and Power for Safety Analyses

The probability of observing a specific AE in this study depends on the number of vaccinated participants with safety follow-up and the underlying incidence of that specific AE in the study population. In seven clinical studies in the 9vHPV program, 356 of 15,778 (2.3%) individuals who were administered 9vHPV vaccine and had safety follow-up reported a SAE; 7 (0.04%) reported at least one SAE determined to be vaccine related [Moreira, E. D., et al 2016]. Assuming that all 200 participants enrolled in this study will have safety follow-up, then there is a 99% chance of observing at least one SAE; and 7.7% chance of observing at least one vaccine related SAE, on at least one of the 200 participants. If no vaccine-related SAEs are observed among the 200 participants, this study will provide 97.5% confidence that the underlying percentage of participants with vaccine-related SAE is <1.8% (1 in every 56 participants) among 9vHPV vaccinated participants. This is based on calculation of a 1-sided 97.5% upper confidence limit of a binomial proportion using the exact binomial method of Clopper and Pearson [Clopper, C. J. and Pearson, E. S. 1934].

10.10 Subgroup Analyses

To determine whether immune response to 9vHPV vaccination is consistent across various subgroups, the percent seroconversion and Month 7 GMTs (with corresponding nominal 95% CIs) will be estimated and Forest plots will be produced for the age subgroups of 9 to 15 years old; 16 to 26 years old.

The consistency of immune response to 9vHPV vaccination will be assessed descriptively via summary statistics by category for the classification variables listed above.

Analysis of immune response to 9vHPV vaccination by gender is not required because in previous studies of the 9vHPV vaccine (Protocols V503-002 and V503-003 [Van Damme, P., et al 2015] [Castellsague, X., et al 2015]), HPV antibody response was similar between genders.

10.11 Compliance (Medication Adherence)

Compliance in this study is defined as receipt of all 3 doses of 9vHPV vaccine. To summarize compliance, the numbers of participants who receive each vaccination will be tabulated. For each of vaccination doses 2 and 3, histograms of the time (in days) of administration of the vaccine relative to the target vaccination visit will be provided.

12.1 Appendix 1: Study Governance Considerations

Merck Code of Conduct for Clinical Trials

Merck*
Code of Conduct for Clinical Trials

I. Introduction

A. Purpose

Merck, through its subsidiaries, conducts clinical trials worldwide to evaluate the safety and effectiveness of our products. As such, we are committed to designing, implementing, conducting, analyzing and reporting these trials in compliance with the highest ethical and scientific standards. Protection of participant safety is the overriding concern in the design of clinical trials. In all cases, Merck clinical trials will be conducted in compliance with local and/or national regulations and in accordance with the ethical principles that have their origin in the Declaration of Helsinki.

B. Scope

Such standards shall be endorsed for all clinical interventional investigations sponsored by Merck irrespective of the party (parties) employed for their execution (eg, contract research organizations, collaborative research efforts). This Code is not intended to apply to trials which are observational in nature, or which are retrospective. Further, this Code does not apply to investigator-initiated trials which are not under the control of Merck.

II. Scientific Issues

A. Trial Conduct

1. Trial Design

Except for pilot or estimation trials, clinical trial protocols will be hypothesis-driven to assess safety, efficacy and/or pharmacokinetic or pharmacodynamic indices of Merck or comparator products. Alternatively, Merck may conduct outcomes research trials, trials to assess or validate various endpoint measures, or trials to determine participant preferences, etc.

The design (ie, participant population, duration, statistical power) must be adequate to address the specific purpose of the trial. Research participants must meet protocol entry criteria to be enrolled in the trial.

2. Site Selection

Merck selects investigative sites based on medical expertise, access to appropriate participants, adequacy of facilities and staff, previous performance in Merck trials, as well as budgetary considerations. Prior to trial initiation, sites are evaluated by Merck personnel to assess the ability to successfully conduct the trial.

3. Site Monitoring/Scientific Integrity

Trial sites are monitored to assess compliance with the trial protocol and general principles of Good Clinical Practice. Merck reviews clinical data for accuracy, completeness and consistency. Data are verified versus source documentation according to standard operating procedures. Per Merck policies and procedures, if fraud, misconduct or serious GCP-non-Compliance are suspected, the issues are promptly investigated. When necessary, the clinical site will be closed, the responsible regulatory authorities and ethics review committees notified and data disclosed accordingly.

B. Publication and Authorship

To the extent scientifically appropriate, Merck seeks to publish the results of trials it conducts. Some early phase or pilot trials are intended to be hypothesis-generating rather than hypothesis testing. In such cases, publication of results may not be appropriate since the trial may be underpowered and the analyses complicated by statistical issues of multiplicity.

Merck's policy on authorship is consistent with the requirements outlined in the ICH-Good Clinical Practice guidelines. In summary, authorship should reflect significant contribution to the design and conduct of the trial, performance or interpretation of the analysis, and/or writing of the manuscript. All named authors must be able to defend the trial results and conclusions. Merck funding of a trial will be acknowledged in publications.

III. Participant Protection

A. IRB/IEC review

All clinical trials will be reviewed and approved by an independent IRB/IEC before being initiated at each site. Significant changes or revisions to the protocol will be approved by the IRB/IEC prior to implementation, except that changes required urgently to protect participant safety and well-being may be enacted in anticipation of IRB/IEC approval. For each site, the IRB/IEC and Merck will approve the participant informed consent form.

B. Safety

The guiding principle in decision-making in clinical trials is that participant welfare is of primary importance. Potential participants will be informed of the risks and benefits of, as well as alternatives to, trial participation. At a minimum, trial designs will take into account the local standard of care. Participants are never denied access to appropriate medical care based on participation in a Merck clinical trial.

All participation in Merck clinical trials is voluntary. Participants are enrolled only after providing informed consent for participation. Participants may withdraw from a Merck trial at any time, without any influence on their access to, or receipt of, medical care that may otherwise be available to them.

C. Confidentiality

Merck is committed to safeguarding participant confidentiality, to the greatest extent possible. Unless required by law, only the investigator, sponsor (or representative) and/or regulatory authorities will have access to confidential medical records that might identify the research participant by name.

D. Genomic Research

Genomic Research will only be conducted in accordance with informed consent and/or as specifically authorized by an Ethics Committee.

IV. Financial Considerations

A. Payments to Investigators

Clinical trials are time- and labor-intensive. It is Merck's policy to compensate investigators (or the sponsoring institution) in a fair manner for the work performed in support of Merck trials. Merck does not pay incentives to enroll participants in its trials. However, when enrollment is particularly challenging, additional payments may be made to compensate for the time spent in extra recruiting efforts.

Merck does not pay for participant referrals. However, Merck may compensate referring physicians for time spent on chart review to identify potentially eligible participants.

B. Clinical Research Funding

Informed consent forms will disclose that the trial is sponsored by Merck, and that the investigator or sponsoring institution is being paid or provided a grant for performing the trial. However, the local IRB/IEC may wish to alter the wording of the disclosure statement to be consistent with financial practices at that institution. As noted above, publications resulting from Merck trials will indicate Merck as a source of funding.

C. Funding for Travel and Other Requests

Funding of travel by investigators and support staff (eg, to scientific meetings, investigator meetings, etc.) will be consistent with local guidelines and practices including, in the U.S., those established by the American Medical Association (AMA).

V. Investigator Commitment

Investigators will be expected to review Merck's Code of Conduct as an appendix to the trial protocol, and in signing the protocol, agree to support these ethical and scientific standards.

* In this document, "Merck" refers to Merck Sharp & Dohme Corp. and Schering Corporation, each of which is a subsidiary of Merck & Co., Inc. Merck is known as MSD outside of the United States and Canada. As warranted by context, Merck also includes affiliates and subsidiaries of Merck & Co., Inc."

Financial Disclosure

Financial Disclosure requirements are outlined in the US Food and Drug Administration Regulations, Financial Disclosure by Clinical Investigators (21 CFR Part 54). It is the Sponsor's responsibility to determine, based on these regulations, whether a request for Financial Disclosure information is required. It is the investigator's/subinvestigator's responsibility to comply with any such request.

The investigator/subinvestigator(s) agree, if requested by the Sponsor in accordance with 21 CFR Part 54, to provide his/her financial interests in and/or arrangements with the Sponsor to allow for the submission of complete and accurate certification and disclosure statements. The investigator/subinvestigator(s) further agree to provide this information on a Certification/Disclosure Form, commonly known as a financial disclosure form, provided by the Sponsor. The investigator/subinvestigator(s) also consent to the transmission of this information to the Sponsor in the United States for these purposes. This may involve the transmission of information to countries that do not have laws protecting personal data.

Data Protection

Participants will be assigned a unique identifier by the sponsor. Any participant records or datasets that are transferred to the sponsor will contain the identifier only; participant names or any information which would make the participant identifiable will not be transferred.

The participant must be informed that his/her personal study-related data will be used by the sponsor in accordance with local data protection law. The level of disclosure must also be explained to the participant.

The participant must be informed that his/her medical records may be examined by Clinical Quality Assurance auditors or other authorized personnel appointed by the sponsor, by appropriate IRB/IEC members, and by inspectors from regulatory authorities.

Confidentiality of Data

By signing this protocol, the investigator affirms to the Sponsor that information furnished to the investigator by the Sponsor will be maintained in confidence, and such information will be divulged to the institutional review board, ethics review committee (IRB/IEC) or similar or expert committee; affiliated institution and employees, only under an appropriate understanding of confidentiality with such board or committee, affiliated institution and employees. Data generated by this study will be considered confidential by the investigator, except to the extent that it is included in a publication as provided in the Publications section of this protocol.

Confidentiality of Participant Records

By signing this protocol, the investigator agrees that the Sponsor (or Sponsor representative), IRB/IEC, or regulatory authority representatives may consult and/or copy study documents in order to verify worksheet/case report form data. By signing the consent form, the participant agrees to this process. If study documents will be photocopied during the process of

verifying worksheet/case report form information, the participant will be identified by unique code only; full names/initials will be masked prior to transmission to the Sponsor.

By signing this protocol, the investigator agrees to treat all participant data used and disclosed in connection with this study in accordance with all applicable privacy laws, rules and regulations.

Confidentiality of IRB/IEC Information

The Sponsor is required to record the name and address of each IRB/IEC that reviews and approves this study. The Sponsor is also required to document that each IRB/IEC meets regulatory and ICH GCP requirements by requesting and maintaining records of the names and qualifications of the IRB/IEC members and to make these records available for regulatory agency review upon request by those agencies.

Publication Policy

The results of this study may be published or presented at scientific meetings. The sponsor will comply with the requirements for publication of study results. In accordance with standard editorial and ethical practice, the sponsor will generally support publication of multicenter studies only in their entirety and not as individual site data. In this case, a coordinating investigator will be designated by mutual agreement.

If publication activity is not directed by the sponsor, the investigator agrees to submit all manuscripts or abstracts to the sponsor before submission. This allows the sponsor to protect proprietary information and to provide comments.

Authorship will be determined by mutual agreement and in line with International Committee of Medical Journal Editors authorship requirements.

Compliance with Study Registration and Results Posting Requirements

Under the terms of the Food and Drug Administration Amendments Act (FDAAA) of 2007 and the European Medicines Agency (EMA) clinical trial Directive 2001/20/EC, the Sponsor of the study is solely responsible for determining whether the study and its results are subject to the requirements for submission to <http://www.clinicaltrials.gov>, www.clinicaltrialsregister.eu or other local registries. MSD, as Sponsor of this study, will review this protocol and submit the information necessary to fulfill these requirements. MSD entries are not limited to FDAAA or the EMA clinical trial directive mandated trials. Information posted will allow participants to identify potentially appropriate studies for their disease conditions and pursue participation by calling a central contact number for further information on appropriate study locations and site contact information.

By signing this protocol, the investigator acknowledges that the statutory obligations under FDAAA, the EMA clinical trials directive or other locally mandated registries are that of the Sponsor and agrees not to submit any information about this study or its results to those registries.

Compliance with Law, Audit and Debarment

By signing this protocol, the investigator agrees to conduct the study in an efficient and diligent manner and in conformance with this protocol; generally accepted standards of Good Clinical Practice (eg, International Conference on Harmonization of Technical Requirements for Registration of Pharmaceuticals for Human Use Good Clinical Practice: Consolidated Guideline and other generally accepted standards of good clinical practice); and all applicable federal, state and local laws, rules and regulations relating to the conduct of the clinical study.

The Code of Conduct, a collection of goals and considerations that govern the ethical and scientific conduct of clinical investigations sponsored by MSD, is provided in this appendix under the Merck Code of Conduct for Clinical Trials.

The investigator agrees not to seek reimbursement from participants, their insurance providers or from government programs for procedures included as part of the study reimbursed to the investigator by the Sponsor.

The investigator will promptly inform the Sponsor of any regulatory authority inspection conducted for this study.

The Investigator agrees to provide the Sponsor with relevant information from inspection observations/findings to allow the Sponsor to assist in responding to any citations resulting from regulatory authority inspection, and will provide the Sponsor with a copy of the proposed response for consultation before submission to the regulatory authority.

Persons debarred from conducting or working on clinical studies by any court or regulatory authority will not be allowed to conduct or work on this Sponsor's studies. The investigator will immediately disclose in writing to the Sponsor if any person who is involved in conducting the study is debarred or if any proceeding for debarment is pending or, to the best of the investigator's knowledge, threatened.

Data Quality Assurance

All participant data relating to the study will be recorded on printed or electronic CRF unless transmitted to the sponsor or designee electronically (eg, laboratory data). The investigator or qualified designee is responsible for verifying that data entries are accurate and correct by physically or electronically signing the CRF.

Detailed information regarding Data Management procedures for this protocol will be provided separately.

The investigator must maintain accurate documentation (source data) that supports the information entered in the CRF.

The investigator must permit study-related monitoring, audits, IRB/IEC review, and regulatory agency inspections and provide direct access to source data documents.

Study documentation will be promptly and fully disclosed to the Sponsor by the investigator upon request and also shall be made available at the study site upon request for inspection, copying, review and audit at reasonable times by representatives of the Sponsor or any

regulatory authorities. The investigator agrees to promptly take any reasonable steps that are requested by the Sponsor or regulatory authority as a result of an audit or inspection to cure deficiencies in the study documentation and worksheets/case report forms.

The sponsor or designee is responsible for the data management of this study including quality checking of the data.

Study monitors will perform ongoing source data review and verification to confirm that data entered into the CRF by authorized site personnel are accurate, complete, and verifiable from source documents; that the safety and rights of participants are being protected; and that the study is being conducted in accordance with the currently approved protocol and any other study agreements, ICH GCP, and all applicable regulatory requirements.

Records and documents, including signed ICF, pertaining to the conduct of this study must be retained by the investigator for 15 years after study completion unless local regulations or institutional policies require a longer retention period. No records may be destroyed during the retention period without the written approval of the sponsor. No records may be transferred to another location or party without written notification to the sponsor.

Source Documents

Source documents provide evidence for the existence of the participant and substantiate the integrity of the data collected. Source documents are filed at the investigator's site.

Data reported on the CRF or entered in the eCRF that are transcribed from source documents must be consistent with the source documents or the discrepancies must be explained. The investigator may need to request previous medical records or transfer records, depending on the study. Also, current medical records must be available.

Study and Site Closure

The sponsor or its designee may stop the study or study site participation in the study for medical, safety, regulatory, administrative, or other reasons consistent with applicable laws, regulations, and GCP.

In the event the Sponsor prematurely terminates a particular study site, the Sponsor will promptly notify that study site's IRB/IEC.

12.2 Appendix 2: Adverse Events: Definitions and Procedures for Recording, Evaluating, Follow-up, and Reporting

Definition of AE

AE Definition

- An AE is any untoward medical occurrence in a patient or clinical study participant, temporally associated with the use of study treatment, whether or not considered related to the study treatment.
- NOTE: An AE can therefore be any unfavorable and unintended sign (including an abnormal laboratory finding), symptom, or disease (new or exacerbated) temporally associated with the use of a study treatment.
